### **6.8.1. Individualized Treatment Regimen**

In addition to the option to switch to the optional cohort in Group B and withdrawal from the study, individualized treatment regimen was set up to as a regimen that may be used when participants are judged to have difficulty continuing their designated treatment regimen due to failure to respond (based on non-conversion supported by microbiological results, and clinical worsening of symptoms related to MAC-LD supported by the results such as chest computed tomography [CT] scan) or the occurrence of AE.

During the study, if deemed necessary by the investigator to switch to individualized treatment regimen (in principle, add on SM, injectable or inhalation suspension of AMK. Regimens that may be selected for each treatment group are listed below) and continue treatment, it can be done by obtaining re-consent from the participant (refer to Sections 1.2 and 4.1). Participants should meet one of the following criteria to switch to individualized treatment regimen. (Note: Refer to Section 6.3 for blinding method of the microbiological assessment result).

- Continuation of assigned treatment regimen is difficult because participants are non-converters based on the result of microbiological test (ie, positive) and have clinical worsening of symptom associated with MAC-LD based on the findings in chest CT scan and so on, at the discretion of investigators.
- Continuation of assigned treatment regimen is difficult due to AE related to drug in assigned regimen, at the discretion of investigators.

Individualized treatment regimens permitted in this study are described in below. Investigators should select the appropriate regimens for participants in each treatment group or if no regimen is considered appropriate the participants should be discontinued from the study.

#### **Group A (Assigned treatment regimen: BDQ + CAM + EB)**

- BDQ + CAM + EB + aminoglycosides (add one of injectable SM, injectable or inhalation suspension of AMK)
- BDQ + CAM + aminoglycosides (same as above)
- BDQ + CAM (when difficult to continue treatment with EB and no clinical worsening)

#### **Group B (Assigned treatment regimen: Rifamycin + CAM + EB)**

- Rifamycin + CAM + EB + aminoglycoside (same as above)

- Rifamycin+ CAM + aminoglycoside (same as above)
- Rifamycin + CAM (when difficult to continue treatment with EB and no clinical worsening)

Note: From the viewpoint of preventing the development of CAM resistance, a regimen with EB discontinuation should be carefully considered.

If an investigator judges that it is necessary to use treatment regimens other than those listed above, such as discontinuation of study intervention, discontinuation of CAM or switching CAM to AZM (prohibited medication), the participant should be discontinued from the study and treatment regimens available at the study site will be provided.

Prior to switching to an individualized treatment regimen, visit and assessments for switch to individualized treatment regimen must be done as shown in Section 1.3, [Schedule of Activities \(SoA\)](#). After switching, a participants will continue their usual schedule for assigned treatment regimen. Note that participants in Group A who have switched to individualized treatment regimen can continue up to Week 48, participants in Group B can continue up to Week 60.

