In South Korea, "KOREAN GUIDELINE FOR TUBERCULOSIS 4th EDITION" is published in 2020, and in Taiwan, "Consensus Statement of Nontuberculous Mycobacterial Lung Disease in Taiwan" is published in 2020. Both diagnostic criteria for NTM-LD and chemotherapy for MAC-LD in both countries are in accordance with an official ATS/IDSA statement, and chemotherapy mainly with 3 drugs consisted of macrolide (CAM or AZM), rifamycin (RFP or RBT), and EB, is recommended as the standard therapy.

In addition, the inclusion of RBT or RFP, a moderate or strong inducer of hepatic cytochrome P450 (CYP) 3A4 enzymes, in the MAC-LD treatment regimen complicates the administration of other important drugs to treat underlying conditions in patients with MAC-LD.

For the most comprehensive nonclinical and clinical information regarding BDQ, refer to the latest version of the Investigator's Brochure (IB) addendum, and local package insert of SIRTURO (BDQ).

The term “study drug” throughout the protocol refers to BDQ. The term “study intervention” throughout the protocol refers to BDQ and rifamycin (RFP or RBT) as defined in Section 6.1, [Study Interventions Administered](#).

The term "sponsor" used throughout this document refers to the entities listed in the Protocol Supplementary Information, which will be provided as a separate document.

The term "participant" throughout the protocol refers to the common term "subject".

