## Clinical Studies

### *Phase 1 Studies*

Pooled analyses were done for 8 Phase 1 studies in healthy subjects (5 single-dose studies and 3 multiple-dose studies). The pooled analysis included data from 217 healthy subjects, of whom, 189 received at least 1 dose of BDQ up to 700 mg. Five studies were not included in the Phase 1 pooled analysis: C117 was an open-label, DDI study in 16 HIV-1 infected subjects (without TB infection). This single-sequence DDI Phase 1 study was conducted to investigate the potential interaction between steady-state nevirapine and a single-dose of 400 mg BDQ. C112 was an open-label, single-dose study in 8 healthy subjects and in 8 subjects with moderate hepatic impairment. TBC1003 was a double-blind, single-dose study in 88 healthy subjects to evaluate the effect of a single supratherapeutic (800 mg) dose BDQ on the QT/corrected QT (QTc) interval. A total of 44 subjects received BDQ. TBC1002 was an open-label 3-way crossover study in 36 healthy adults to assess the relative bioavailability of 2 pediatric formulations of BDQ after single-dose administration of 100 mg, with and without food. NTM1001 was an open-label, DDI study in 16 healthy subjects. This single-sequence DDI Phase 1 study was conducted to investigate the potential interaction between steady-state CAM and a single-dose of 100 mg BDQ.

Bedaquiline was well absorbed with  $t_{\max}$  at approximately 5 hours postdose. The  $C_{\max}$  and AUC increased proportionally up to the highest doses studied (700 mg single dose and 400 mg once daily [qd] multiple doses). Accumulation from Day 1 to Day 14 was approximately 2-fold expressed as increase in AUC, corresponding to an effective half-life of about 24 hours. From Phase 2 study, 4 weeks after ceasing BDQ intake, the mean BDQ and M2 concentrations were reduced by approximately 40% compared to the end of the BDQ treatment period. At the last follow-up visit (Week 120), BDQ and M2 plasma concentrations were approximately 15% and 20% of the median Week 24 plasma concentrations, respectively. The average  $t_{1/2 \text{ term}}$  of BDQ and M2, was estimated as 5.5 months and 5.3 months, respectively.

Administration of BDQ as the tablet formulation with food increased the relative bioavailability (by 95%) compared to administration without food.

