### **7.2. Participant Discontinuation/Withdrawal From the Study**

A participant will NOT be automatically withdrawn from the study if he or she has to discontinue study intervention before Week 48 (Group A), Week 60 (Group B), or OPW48 (the optional cohort). A participant will be withdrawn from the study for any of the following reasons:

- Lost to follow-up
- Withdrawal of consent
- Death

When a participant withdraws before study completion, the reason for withdrawal is to be documented in the eCRF and in the source document.

Participants will be encouraged to complete the early discontinuation visit assessments, which is to be scheduled within 7 days of investigator's discretion to discontinue treatment with study intervention. If the reason for withdrawal from the study is withdrawal of consent, then no additional assessments are allowed.

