##### ***AST and/or ALT Elevation***

$<5.0 \times$  ULN AST or ALT elevation with normal bilirubin:

Participants may continue to take the study intervention. Participants should be followed until resolution (return to baseline) or stabilization of AST/ALT elevation. Clinical symptoms, AST,

ALT, and serum bilirubin should be monitored every 2 weeks until clinically stable as necessary to manage the participant's condition.

$\geq 5.0 \times \text{ULN}$  but  $\leq 8.0 \times \text{ULN}$  AST or ALT elevation or  $\geq 3 \text{ ULN}$  accompanied by bilirubin  $\geq 2.0 \times \text{ULN}$ :

Participants will be permanently discontinued from treatment of the suspected causative background agent or temporarily withhold study intervention at the investigator's discretion. Clinical symptoms, AST, ALT, and serum bilirubin should be monitored every 2 weeks until clinically stable as necessary to manage the participant's condition. If ALT, AST, and bilirubin do not improve or worsens within 2 weeks, the study intervention will be temporarily withheld for up to 2 weeks per investigator discretion. Additional tests should be performed to evaluate the cause of hepatitis (eg, hepatitis A, B, C). Liver enzymes, including serum bilirubin should be monitored as frequently as necessary to manage the participant's condition. If AST/ALT decreases to  $< 5.0 \times \text{ULN}$ , study intervention can be restarted once. Participants who fail to show improvement, demonstrated by no improvement in clinical course or persistent AST and ALT  $\geq 5.0 \times \text{ULN}$  values, or persistent AST/ALT  $\geq 3.0 \times \text{ULN}$  accompanied by bilirubin  $\geq 2.0 \times \text{ULN}$  (over 4 weeks) will have to permanently discontinue the study intervention. Participants should be followed until resolution or stabilization (return to baseline) of AST/ALT/bilirubin elevation.

$> 8.0 \times \text{ULN}$  AST or ALT elevation

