Per investigator discretion, the study intervention will be temporarily withheld for up to 2 weeks. Additional tests should be performed to evaluate the cause of hepatitis (eg, hepatitis A, B, C). Liver enzymes, including serum bilirubin should be monitored as frequently as necessary to manage the participant's condition. If AST/ALT decreases to  $< 5.0 \times \text{ULN}$ , study intervention can be restarted one time. Participants who fail to show improvement, demonstrated by no improvement in clinical course or persistent AST and ALT  $\geq 5.0 \times \text{ULN}$  values, or persistent AST/ALT  $\geq 3 \times \text{ULN}$  accompanied by bilirubin  $\geq 2.0 \times \text{ULN}$  will have to permanently discontinue the study intervention but can continue the study procedures. Participants should be followed until resolution or stabilization (return to baseline) of AST/ALT elevation.

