### ***Musculoskeletal System and Cardiac Muscle***

#### **Myalgia**

Grade 1 (with no limitation of activity):

Participants may continue to take the study intervention and should be carefully evaluated and followed closely.

Grade 2 (muscle tenderness at site other than injection site or with moderate impairment of activity) or Grade 3 (severe muscle tenderness with marked impairment of activity) or Grade 4 (frank myonecrosis):

Participants will have to permanently discontinue the study intervention but can continue in the study. Creatinine phosphokinase should be fractionated for creatine kinase myocardial band (CPK-MB) subunit. Participants having confirmed  $\geq$ Grade 2 myalgia with Grade 3 ( $3.0$  to  $6.0 \times$  ULN) elevation in CPK-MB, or Grade 4 ( $>6.0 \times$  ULN) elevation in CPK-MB subunit will have to permanently discontinue the study intervention.

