## Analysis Phase

Analysis phase	Start date	End date
Screening	The date of signing the informed consent	1 day before the first study intervention intake
Investigation	Date of the first study intervention intake	If the participants are from Group A, Min [Week 48, study discontinuation]
		If the participants from Group B will not convert to the optional cohort, Min [Week 60, study discontinuation]
		If the participants will convert to the optional cohort, 1 day before the optional investigation phase
Optional investigation	Date of the first BDQ+CAM+EB intake for nonconverters came from Group B	For nonconverters came from Group B, Min [Optional Week 48, study discontinuation]
Follow-up	If the participants are in Group A and moved to follow-up period, end of the investigation phase + 1 day	Min [Week 60, study discontinuation]

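### Protocol 6.8.1 takes participants who stop study intervention out of the study while 7.2 and parts of 8.2.6 let them stay, so scheduled follow-up can be selectively shorter in those who stopped for toxicity

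*Protocol*

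**What the plan says.** Protocol 6.8.1 lists the individualized regimens allowed in each group. If the investigator needs anything else, "such as discontinuation of study intervention, discontinuation of CAM or switching CAM to AZM (prohibited medication), the participant should be discontinued from the study". Participants who stay within the list, for example by dropping ethambutol or adding an aminoglycoside, keep their usual visit schedule.

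Protocol 7.2 says: "A participant will NOT be automatically withdrawn from the study if he or she has to discontinue study intervention" before the planned end of treatment. It gives three reasons for withdrawal: loss to follow-up, withdrawn consent and death.

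Protocol 8.2.6 says of AST/ALT above 8 times the upper limit without improvement that participants "will have to permanently discontinue the study intervention but can continue the study procedures", and of Grade 2 to 4 myalgia: "Participants will have to permanently discontinue the study intervention but can continue in the study". For the AST/ALT tier from 5 to 8 times the limit it says: "Participants will be permanently discontinued from treatment of the suspected causative background agent or temporarily withhold study intervention at the investigator's discretion". Nothing there mentions leaving the study.

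In the Introduction, the term study intervention "throughout the protocol refers to BDQ and rifamycin (RFP or RBT) as defined in Section 6.1". CAM is not included.

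SAP 5.1 ends the Group A investigation phase at "Min [Week 48, study discontinuation"; the rule for Group B participants who do not enter the optional cohort has the same form with Week 60. SAP 5.6.2 counts an adverse event as treatment-emergent only up to the end of that phase.

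**The concern.** Consider a participant who stops bedaquiline for myalgia at Week 8. Under 7.2 and 8.2.6 the participant may remain in the study. Under 6.8.1 the participant leaves it. Both texts are current, so the length of observation depends on which section the site follows.

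The participants affected are not a random subset. They are largely those who could not tolerate the drug, whereas those who only drop ethambutol or add an aminoglycoside stay on the full schedule. Two analyses are exposed:

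- **Adverse events.** SAP 5.6.2 tabulates numbers and percentages of participants with an event, by phase. A shorter window gives less opportunity to record a new event. The protocol's own pharmacokinetic summary (2.2) makes the period after stopping relevant: "4 weeks after ceasing BDQ intake, the mean BDQ and M2 concentrations were reduced by approximately 40" percent, with a terminal half-life of about 5.5 months.
- **SGRQ at Week 24.** SAP 5.4.2.2.6 specifies an ANCOVA on change from baseline. It gives no strategy for treatment discontinuation, and the imputation rule in 5.4.2.1 covers only a partly missing score.

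**Working it through.** **1. The plan's own figure.** Inputs from Protocol 9.2: 62 per arm, 10% versus 30%, two-sided 5%, chi-square test. With pooled variance under the null and no continuity correction, z = (0.20 × √62 − 1.96 × √(2 × 0.20 × 0.80)) / √(0.30 × 0.70 + 0.10 × 0.90) = (1.575 − 1.109) / 0.548 = 0.851, which gives power 0.803. The stated figure of about 80% reproduces. It does not depend on this point: Protocol 9.4.2 counts discontinuation before Week 24 as non-conversion whether the participant leaves or stays.

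**2. The texts side by side.**

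- Stopping bedaquiline or rifamycin: 6.8.1 directs study exit; 7.2 says exit is not automatic; 8.2.6 permits continuation in the tier above 8 times the upper limit and for Grade 2 to 4 myalgia. This conflict is explicit.
- Stopping CAM: 6.8.1 directs study exit. Neither 7.2 nor the two permissive tiers of 8.2.6 name CAM. The conflict is inferred from the three reasons in 7.2 and from the background-agent sentence in 8.2.6.
- Regimen changes generally: 1.3 footnote b and 4.1 say such participants are followed for safety, with all assessments performed as in the protocol. This sits awkwardly with exit for regimens outside the list.

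**3. What remains after exit under 6.8.1.**

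- An early discontinuation visit within 7 days (1.3 footnote f; 7.1), with ECG, physical examination, vital signs and laboratory tests required, and SGRQ, lung function, CT, visual and hearing tests only if available.
- Serious adverse event reporting to 30 days after the last dose (8.3.1).
- Follow-up of persisting abnormalities (8.2) and unresolved serious events (10.4.5).
- Weekly ECGs until resolution after a QTcF stop (8.2.3), and AST/ALT follow-up to resolution or stabilization (8.2.6).

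What ceases is the routine schedule: ECG, laboratory tests, vital signs and collection of new non-serious adverse events.

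**4. Length of schedule affected (illustration).** A Group A participant who stops and leaves at Week 8 has 48 − 8 = 40 weeks to Week 48, and 60 − 8 = 52 weeks to the end of the schedule. The 30-day window is 30 / 7 = 4.3 weeks, and 4.3 / 52 is about 8%.

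**5. Week 24 SGRQ.** SAP Table 2 opens the Week 24 window on Day 157 (157 / 7 = 22.4 weeks) and closes it on Day 184. A score from an early discontinuation visit counts as Week 24 only within those days. Let d be the proportion who stop and leave before Day 157. The documents give no value, so a range is assumed. Scores per arm = 62 × (1 − d). At constant standard deviation, the confidence interval widens by 1 / √(1 − d).

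| Assumed d | Scores per arm | Widening factor |
|---|---|---|
| 5% | 58.9 | 1.03 |
| 10% | 55.8 | 1.05 |
| 20% | 49.6 | 1.12 |
| 30% | 43.4 | 1.20 |

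The loss of precision is modest over most of this range. The selection of who is missing matters more.

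**The case against.** The strongest reply is that little is lost. The event that caused the stop is already counted, because the tables count participants with at least one occurrence. The required safety assessments and continuing follow-up in step 3 cover much of what would be expected for QTcF and liver stops. SGRQ is a supportive secondary endpoint, and SAP 5.4.1 defines no confirmatory secondaries. All of this stands. It confines the loss to new events that routine visits would have found, and to Week 24 SGRQ scores.

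Nor does 7.2 guarantee good data. It says only that withdrawal is not automatic, sets no off-treatment schedule and points to the same early discontinuation visit. The two tiers of 8.2.6 grant permission, and the other permanent-stop tiers do not say whether the participant stays. This also stands, and it is a reason for one clear statement of which visits continue.

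Four stronger readings may tempt a reader; the documents support none of them:

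- That all later safety data are lost: step 3 shows otherwise.
- That 7.2 and 8.2.6 expressly keep in a participant who stops CAM: the definition of study intervention excludes CAM.
- That loss differs by arm, or that the ECG and liver results will look too favorable: no rate by arm is given, and those two areas have their own follow-up after stopping.
- That the 40% fall applies unchanged to an early stopper: it was measured from the end of the Phase 2 treatment period, so that use is extrapolation.

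**Conclusion.** The contradiction between 6.8.1 and 7.2/8.2.6 over stopping study intervention is real, explicit and in current text; for CAM it is by implication. Where 6.8.1 is followed, routine visits end after the early discontinuation visit, the treatment-emergent window closes at study discontinuation, and participants leaving before about Day 157 contribute no Week 24 SGRQ score. The shortening falls selectively on participants who stopped for toxicity and can vary by site.

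The size is uncertain. At an assumed 5% to 30% stopping and leaving before Day 157, about 3 to 19 of 62 per arm would lack the Week 24 score, taking every such stopper to leave under 6.8.1. A reader might infer that the primary result is at risk; it is not, because the composite strategy gives the same outcome under either rule. The point is worth correcting, but it concerns secondary and safety analyses.

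**What to change.** Reconcile 6.8.1 (including its earlier sentence discontinuing participants for whom no listed regimen is suitable), 7.2 and 8.2.6, so that discontinuing study intervention or CAM is separated from discontinuing the study. Give one statement of which already scheduled data-collection visits (adverse events, safety assessments, SGRQ) continue after stopping, for participants who agree. Check the result against 1.2 footnote c, 1.3 footnote b and 4.1. Simply limiting withdrawal to the three reasons in 7.2 would not work: 1.2 footnote c and 4.1 also discontinue Group A non-converters at Week 48 who continue chemotherapy.

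In the SAP, state in 5.1 and 5.6.2 how adverse events after the stop are attributed, and in 5.4.2.2.6 which strategy the Week 24 SGRQ ANCOVA uses for treatment discontinuation.

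The cost is a protocol amendment touching several sections, with ethics review and any consent-form revision, plus short SAP text. The visits already exist in the schedule, and some participants will decline them. If conduct is too advanced to amend the protocol, the SAP and study report can still state which rule each such participant followed. No stopping criterion, treatment or clinical monitoring rule is proposed.

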### 6.8.2. Optional Cohort

To maximize the benefit and minimize the risk, participants in treatment Group B can switch to optional cohort after completion of Week 24 assessment. The decision to switch to optional cohort can be made by Week 32 (refer to Sections 1.2, 1.3 and 4.1). Participants must meet all of the following criteria at the timing of the decision to switch to optional cohort. Before starting BDQ administration, a washout of rifamycin for 2 weeks is required and BDQ administration in optional cohort should start by OPD1.

- Participants are non-converter based on the result of microbiological test (ie, positive) up to Week 24.
- Participants do not have condition described in Section 7.1.
- Participants do not experience any AE associated with CAM and/or EB that causes discontinuation of CAM and/or EB at the discretion of investigators.

Switching from an individualized treatment regimen to the optional cohort is not permitted.

Switching to an individualized treatment regimen is permitted if the criteria described in Section 6.8.1 are met, even after switching to the optional cohort.

## 7. DISCONTINUATION OF STUDY INTERVENTION AND PARTICIPANT DISCONTINUATION/WITHDRAWAL

### 7.1. Discontinuation of Study Intervention

A participant's study intervention must be discontinued if:

- The participant withdraws consent to receive study intervention.
- The investigator believes that for safety reasons or tolerability reasons (eg, AE) it is in the best interest of the participant to discontinue study intervention.

- The participant has a QTcF prolongation (defined as a QTcF value  $\geq 500$  ms, or an increase from baseline of  $>60$  ms) at any given time point (confirmed by repeat ECGs).
- The participant requires treatment with any of the prohibited medications listed in Section 6.8, [Concomitant Therapy](#).
- The participant becomes pregnant. Refer to Section 10.5, [Appendix 5: Contraceptive Guidance](#).
- Noncompliance with study intervention administration as defined in [Table 3](#).
- The participants discontinued administration of study intervention before Week 48 in Group A, Week 60 in Group B or OPW48 in optional cohort.

If a participant discontinues study intervention before Week 48 in Group A, Week 60 in Group B or OPW48 in the optional cohort, the participant will receive the assessments of early discontinuation or withdrawal.

The early discontinuation visit assessment will be performed within 7 days of the investigator's discretion to discontinue treatment with study intervention, unless the participant withdraws consent. Study intervention assigned to the participant who discontinued study intervention may not be assigned to another participant.

